- 3.2.6 Autoimmune disease: Patients with a history of inflammatory bowel disease, including ulcerative colitis and Crohn's Disease, are excluded from this study, as are patients with a history of symptomatic disease (eg, rheumatoid arthritis, systemic progressive sclerosis [scleroderma], systemic lupus erythematosus, autoimmune pneumonitis, autoimmune vasculitis [eg, Wegener's Granulomatosis]) and motor neuropathy considered of autoimmune origin (e.g. Guillain-Barre Syndrome and Myasthenia, Gravis). Patients with Hashimoto's thyroiditis are eligible to go on study.
- 3.2.7 Pregnant or nursing women will be excluded from the study because lenalidomide is an agent with the potential for teratogenic or abortifacient effects.
- 3.2.8 History of severe allergic reactions attributed to compounds of similar chemical or biologic composition to Nivolumab or lenalidomide.
- 3.2.9 Known seropositive for or active viral infection with human immunodeficiency virus (HIV), hepatitis B virus (HBV) or hepatitis C virus (HCV). Patients who are seropositive because of hepatitis B virus vaccine are eligible.
- 3.2.10 Major surgery within 4 weeks of enrollment.
- 3.2.11 Myeloma-related central nervous system involvement.
- 3.2.12 Known Amyloid involvement.
- 3.2.13 Participation in other clinical trials, including those with other investigational agents not included in this trial, within 30 days of the start of this trial and throughout the duration of this trial.
- 3.2.14 Prior CVA with persistent neurological deficit.
- 3.2.15 Inability to tolerate thromboprophylaxis.

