5.4 Management of Clinical Events

5.4.1 Rash

- Symptomatic measures such as antihistamines or corticosteroids (oral or topical) have been successfully used to manage rash and have been used prophylactically in subsequent cycles. The use of a topical, IV, or oral steroid (eg, prednisone \leq 10 mg per day or equivalent) is permitted.
- Management of a Grade 3 rash may require intravenous antihistamines or corticosteroids. Administration of lenalidomide (and/or other causative agent

CONFIDENTIAL

This document is confidential. Do not disclose or use except as authorized.

if given in combination) should be modified per protocol and re-initiated at a reduced level from where rash was noted.

- In line with clinical practice, a dermatology consult that includes a biopsy of Grade 3 or higher rash or any SAE involving rash is recommended. Prophylactic measures should also be considered if a patient has previously developed a rash (eg, using a thick, alcohol-free emollient cream on dry areas of the body or oral or topical antihistamines).
- A rare risk is Stevens-Johnson Syndrome, a severe and potentially life-threatening rash with skin peeling and mouth sores, should be managed symptomatically according to standard medical practice. Punch biopsies for histopathological analysis are encouraged at the discretion of the investigator.

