5.5 Criteria for Taking a Participant Off Protocol Therapy

Patients will be informed that they have the right to withdraw from the study at any time for any reason, without prejudice to their medical care.

In the absence of treatment delays due to adverse event(s), treatment may continue for 12 cycles or until one of the following criteria applies:

- Progression to overt Multiple Myeloma
- Intercurrent illness that prevents further administration of treatment

CONFIDENTIAL

This document is confidential. Do not disclose or use except as authorized.

- Unacceptable adverse event(s)
- Participant demonstrates an inability or unwillingness to comply with the oral medication regimen and/or documentation requirements
- Participant decides to withdraw from the protocol therapy
- General or specific changes in the participant's condition render the participant unacceptable for further treatment in the judgment of the treating investigator

Participants will be removed from the protocol therapy when any of these criteria apply. The reason for removal from protocol therapy, and the date the participant was removed, must be documented in the case report form (CRF). Alternative care options will be discussed with the participant.

A Treatment Ended/Off Study Form will be filled out when a participant is removed from protocol therapy. This form will be provided by the lead site. External sites should submit the form to the Research Project Manager.

In the event of unusual or life-threatening complications, treating investigators must immediately notify the Overall PI, [name] at [contact].

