Allergic reaction or hypersensitivity to Lenalidomide Including Rash related to Lenalidomide	Grade 1 Grade 2 Grade 3 or Grade 4	
Continue to treat- Do NOT OMIT and DO NOT REDUCE therapy
 
Continue to treat- Do NOT OMIT and DO NOT REDUCE therapy
 
Hold lenalidomide Follow at least weekly. If toxicity resolves to \leq grade 2, restart at next lower dose level

Renal/Metabolic For all grades, provide hydration and other supportive care as needed at the discretion of the treating investigator	Grade 1 Grade 2 Grade 3 or Grade 4	
Continue to treat- Do NOT OMIT and DO NOT REDUCE therapy
 
Hold Lenalidomide until < grade 2 and resume treatment at the same dose level If toxicity recurs, dose reduce one dose level at the treating investigator's discretion
 
Hold Lenalidomide until < grade 2 and resume treatment with one dose level reduction If the toxicity remains \geq grade 3, omit dose and restart at subsequent scheduled visit with one dose level

CONFIDENTIAL

This document is confidential. Do not disclose or use except as authorized.

		reduction If treatment-related toxicity occurs on day one of the cycle, the cycle will be delayed.
--	--	---

Diarrhea, Constipation, Nausea, or Vomiting	Grade 1	Continue to treat- Do NOT OMIT and DO NOT REDUCE therapy
	Grade 2	Treat at the discretion of the investigator Provide aggressive supportive care DO NOT REDUCE therapy
	Grade 3	Hold Lenalidomide until toxicity resolves to < grade 2 If the patient has received maximum supportive care, resume therapy with one dose level reduction
	Grade 4	Hold Lenalidomide until toxicity resolves to < grade 2 Resume therapy with one dose level reduction
All other related toxicities not listed previously in this table	Grade 1	Continue to treat- Do NOT OMIT and DO NOT REDUCE therapy
	Grade 2	Continue to treat- Do NOT OMIT and DO NOT REDUCE therapy unless considered to be a clinically significant finding Provide supportive care as needed

CONFIDENTIAL

This document is confidential. Do not disclose or use except as authorized.

	Grade 3	Hold Lenalidomide until toxicity resolves to < grade 2 Resume therapy with one dose level reduction at the discretion of the treating investigator

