7.2.1.3 Adverse Event List for Lenalidomide

Events that have occurred in >10% of individuals treated with lenalidomide include neutropenia, anemia, thrombocytopenia, fatigue, rash, diarrhea, constipation, nausea, loss of appetite, itching, dry skin, muscle cramps, lack or loss of strength, dizziness, insomnia, swelling of the extremities, headache, back and joint pain, fever, cough, upper respiratory infection, and dyspnea.

Events that have occurred in >1% of individuals treated with lenalidomide include risk of DVT, PE, and blood clots that could lead to stroke, heart attack, or organ failure, febrile neutropenia, atrial fibrillation, pneumonia or lung infections, sepsis, dehydration and renal failure.

Events that have occurred in <1% of individuals treated with lenalidomide include rare treatment-emergent adverse events of angioedema, serious skin reactions including Stevens-Johnson syndrome (SJS) and toxic epidermal necrolysis (TEN) or an allergic skin reaction similar to that seen with thalidomide, tumor lysis syndrome (TLS), tumor flare reaction (TFR), and rhabdomyolysis. In addition, lenalidomide has been shown to increase the level of digoxin in the blood in some patients. Patients will be instructed to inform their doctor if taking digoxin.

There may be an increased risk of second cancers in patients who are on lenalidomide maintenance therapy after a bone marrow transplant.

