3.9 Safety Assessments and Toxicity Monitoring

The study teams at all participating institutions are responsible for protecting the safety, rights and well-being of study participants. Recording and reporting of adverse events that occur during the course of a study help ensure the continuing safety of study participants.

All participants receiving investigational agents and/or other protocol mandated therapy will be evaluated for safety. The safety parameters include all laboratory tests and hematological abnormalities, physical examination findings, and spontaneous reports of adverse events reported by participants. All toxicities encountered during the study will be evaluated according to the NCI criteria specified in the protocol. Life-threatening toxicities must be reported immediately to the DF/HCC Sponsor via the Coordinating Center.

Additional safety assessments and toxicity monitoring will be outlined in the protocol.

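### Table 13's written default after Grade 4 lenalidomide hypersensitivity or rash is a restart one dose level lower; neither that grade nor angioedema, SJS or TEN triggers a lenalidomide stop

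*Combined protocol and SAP*

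**What the plan says.** Table 13 in section 6.3 has one row for allergic reaction or hypersensitivity to lenalidomide, rash included. At Grades 1 and 2, dosing continues unchanged. Grades 3 and 4 share a single cell: hold, review at least weekly and, if the reaction falls to or below "grade 2, restart at next lower dose level". The opening text of 6.3 says the table should be followed for events at least possibly related to lenalidomide, unless the overall PI agrees to something else first.

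Section 7.2.1.3 names angioedema, SJS and TEN among reactions seen in under 1% of people given lenalidomide, and attaches no action. Section 5.4.1 describes SJS as "a severe and potentially life-threatening rash with skin peeling and mouth sores, should be managed symptomatically according to standard medical practice". It does not say whether lenalidomide stops. An earlier bullet in that section, on Grade 3 rash, has the drug restarted at a reduced level.

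Several general provisions also apply:
- Section 5.5: "In the event of unusual or life-threatening complications, treating investigators must immediately notify the Overall PI". Appendix E, section 3.9, adds: "Life-threatening toxicities must be reported immediately to the DF/HCC Sponsor via the Coordinating Center".
- Section 5.5 also requires removal from protocol therapy once an adverse event is unacceptable, or once the treating investigator judges the patient unacceptable for further treatment.
- Section 6.1 caps toxicity delays at 3 weeks unless the PI approves longer for a patient who is benefiting. It also requires related non-hematologic toxicity to be at Grade 1 or less, or at baseline, before a new lenalidomide cycle.

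**The concern.** Section 6.2 treats Grade 4 as life-threatening (for example, in its pneumonitis and hepatitis guidance). For lenalidomide hypersensitivity, Table 13 does not separate that grade from Grade 3. A site that follows the row as written gives the patient again the drug held responsible for a life-threatening reaction, at a dose one step lower. Stopping requires someone to go beyond the row or depart from it. What is at stake is the safety of an individual patient. The primary analysis, type I error and power are untouched.

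**Working it through.** The plan has no figure to reproduce here. The check sets the provisions side by side, followed by short arithmetic on dose and reach.

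**1. Is there a lenalidomide stop tied to these events?** Tables 12 and 13 contain no permanent-discontinuation wording. The 21-day off-study sentence appears in the two infection rows and in the Grade 4 cell for toxicities not listed earlier in the table. It is triggered by delay and is absent from the hypersensitivity row. The one explicit event-based lenalidomide stop found is for pregnancy (section 7.5). Stops tied to Grade 4 hypersensitivity or rash, angioedema, SJS or TEN: 0.

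**2. Does it matter which row a named reaction falls in?** If SJS, TEN or angioedema were graded under the catch-all row instead, its Grade 4 cell also resumes lenalidomide one level lower, once toxicity is below Grade 2. Either way the default after Grade 4 is a restart.

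**3. When does the Grade 2 release apply?** Section 6.1 asks for Grade 1 or less, or baseline, on Day 1 of a cycle, so the Grade 2 threshold operates only mid-cycle. This affects when the restart happens. It does not prevent one.

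**4. How are the other study drugs handled?** Table 11 permanently stops nivolumab for a Grade 4 related toxicity not listed elsewhere in that table. Table 15 permanently stops dexamethasone for symptomatic pancreatitis of any grade. A Grade 4 rash attributed to nivolumab therefore ends nivolumab, while the same rash attributed to lenalidomide leads to a restart.

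**5. Restart dose** (Tables 7, 8 and 14, no earlier reduction):
- Induction: 25 mg to 20 mg; 20/25 = 80% of the dose.
- Maintenance: 15 mg to 10 mg; 10/15 = 67%.

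**6. Who can still be affected?** Since September 2017 accrual has been closed and nivolumab stopped, but section 1.1 lets patients elect to stay on lenalidomide. Under section 5.5, "treatment may continue for 12 cycles or until one of the following criteria applies". Assume the latest possible start (September 2017), no delays, and that the 12-cycle limit still applies:
- Length of treatment: 12 × 28 = 336 days.
- Start 1 September 2017: ends 3 August 2018, which is 192 days after the 23 January 2018 version date; 192/28 = 6.9 cycles.
- Start 30 September 2017: ends 1 September 2018, which is 221 days after; 221/28 = 7.9 cycles.

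Under these assumptions the row could still apply for up to about 8 cycles. The documents do not say how many patients remain on lenalidomide.

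**The case against.** The strongest case against is that the protocol does not leave the decision to one table cell. The overall PI is told of a life-threatening event at once and is also the person who can approve a departure from Table 13. Removal under section 5.5 is mandatory once its criteria are met, and the treating investigator can reach that judgement alone. The restart is conditional on recovery, and section 6.1 ends treatment after 3 weeks' delay unless the PI agrees otherwise. Hold-and-reduce after Grade 4 is also a consistent pattern: the gastrointestinal and catch-all rows of Table 13 and the catch-all row of Table 15 use it.

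Much of this stands, and it rules out four stronger readings that a reader might infer.
- *That nothing in the protocol requires a stop.* Sections 5.5 and 6.1 do require one when their conditions are met. What is missing is a stop triggered by the grade or the name of the reaction.
- *That the entry exclusion sets the standard.* Section 3.2.8 excludes patients with "History of severe allergic reactions attributed to compounds of similar chemical or biologic composition to Nivolumab or lenalidomide". This is an entry rule about similar compounds. Section 7.1.2 describes severe as Grade 3 or 4, so using it as the benchmark would also stop Grade 3. It does not yield a Grade 4 line.
- *That every grade of angioedema should stop the drug.* The fault shown lies in the shared Grade 3-4 cell. Nothing here shows the lower-grade lines to be wrong.
- *That whole-trial expected counts give the preventable harm.* Multiplying 41 planned patients by the 1% ceiling gives fewer than 0.41 cases of any one listed reaction (41 × 0.01). That covers the whole planned cohort and all of its treatment. A January 2018 change could affect only patients still on the drug, and section 7.2.1.3 gives no rate for Grade 4 hypersensitivity.

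The consistency argument does not settle the matter. Restarting at a lower dose after Grade 4 diarrhea is a different proposition from re-exposure after a life-threatening hypersensitivity reaction.

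**Conclusion.** The point holds in a limited form. Table 13's written default after Grade 4 lenalidomide hypersensitivity or rash is re-exposure one dose level lower, and no lenalidomide stop is tied to that grade or to angioedema, SJS or TEN. Stopping depends on judgement, on delay beyond 3 weeks, or on an agreed departure from the table. Those routes make an unreviewed restart unlikely without changing the default.

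Practical reach is small, and the preventable number of cases cannot be computed from the documents. The case for change rests on how serious a single re-exposure could be, not on how often one would occur. It also rests on a clinical safety judgement that Grade 4 is the right line, since the documents set no standard for it. This is a cheap improvement.

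**What to change.** Split the Table 13 row:
- **Grade 3 hypersensitivity or rash:** hold, then restart one level lower; on Day 1 of a cycle, only at Grade 1 or less, or baseline, as section 6.1 already requires.
- **Grade 4 hypersensitivity or rash, and SJS, TEN or Grade 3-4 angioedema, attributed to lenalidomide:** permanently discontinue lenalidomide. The named reactions take precedence over the Grade 3 line.

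State the same stop in the SJS bullet of section 5.4.1.

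The cost is a wording change to one row and one bullet, with no new data or procedures. A rare patient would lose the option of lenalidomide re-challenge. The note below Table 13 already lets a patient who stops lenalidomide remain on protocol therapy, so the change need not end participation.

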6. DOSING DELAYS/DOSE MODIFICATIONS

6.1 Recommended Criteria for Beginning or Delaying a Subsequent Treatment Cycle

Patients must meet eligibility criteria on Cycle 1 Day 1 to begin treatment. There are no pre-treatment criteria to begin a new cycle of nivolumab.

For a new cycle of treatment with lenalidomide to begin, the patient must meet the following criteria:

- ANC must be $\geq 1,000/\mu\text{L}$.
- Platelet count must be $\geq 50,000/\mu\text{L}$.
- All other clinically significant, study drug related non hematologic toxicity must have resolved to \leq Grade 1 or to baseline condition

If the participant fails to meet the above-cited criteria for initiation of a new cycle of treatment on day 1 of the cycle, dosing of all medications should be delayed for 1 week. At the end of that time, the participant should be re-evaluated to determine whether the above criteria have been met. If the participant continues to fail to meet the above-cited criteria, delay therapy and continue to re-evaluate. The maximum delay for toxicity related to study treatment before treatment is permanently discontinued will be 3 weeks. If a delay of > 3 weeks is clinically necessary, and the patient is showing benefit from treatment, the patient may continue on study after discussion and approval by the Principal Investigator.

If any one of the study medications is permanently discontinued for any reason including toxicity, or FDA mandate, the patient may remain on the study at the discretion of the principal investigator.

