6.3 Lenalidomide

Hematologic Toxicities: For adverse hematologic events that are considered possibly, probably or definitely related to Lenalidomide, the following criteria for retreatment and dose modification should be followed unless discussed and approved first by the overall principal

CONFIDENTIAL

This document is confidential. Do not disclose or use except as authorized.

investigator. The treating investigator should determine the clinical significance of laboratory values and attribution to study medications before a treatment decision is made. All instances where lenalidomide is held, the dose will be considered missed, and will not be made up.

Non Hematologic Toxicity: For adverse non hematologic events that are considered to be possibly, probably or definitely related to Lenalidomide, the following criteria for retreatment and dose modification should be followed unless discussed and approved first by the overall principal investigator. The treating investigator should determine the clinical significance of laboratory values or radiographic findings and attribution to study medications before a treatment decision is made. All instances where lenalidomide is held, the dose will be considered missed, and will not be made up.

Dose delays and modifications should be made as indicated in the following table(s) unless first discussed with the Overall PI. The descriptions and grading scales found in the revised NCI Common Terminology Criteria for Adverse Events (CTCAE) version 4.0 will be utilized for dose delays and dose modifications. A copy of the CTCAE version 4.0 can be downloaded from the CTEP website

http://ctep.cancer.gov/protocolDevelopment/electronic_applications/ctc.htm.

Table 12 Lenalidomide Hematologic Toxicities

CTCAE 4.0 Category	CTCAE Grade	Lenalidomide Dose Modification
Absolute Neutrophil Count (ANC)¹	Grade 1 or Grade 2	Continue to treat- Do NOT OMIT and DO NOT REDUCE therapy
	Grade 3	Hold dose Administer Filgrastim Resume at same dose when ANC is \geq 1000 if neutropenia is the only hematologic toxicity If other hematologic toxicity \geq Grade 2 is present, reduce dose one level when ANC \geq 1000
	Grade 4	Hold dose Administer Filgrastim Resume therapy at one dose level lower when ANC is \geq 1000
Neutropenia with Fever ANC <1000 and temperature \geq 38.5° C or 101°F	Grade 3 or Grade 4	Hold dose Administer Filgrastim Reduce dose one level when ANC \geq 1000

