6.5 Dose Delay Guidelines

Required study schedule assessments should always correlate with the nivolumab dosing schedule. If lenalidomide and/or dexamethasone are held during a cycle, then study assessments should continue per the schedule of assessments in Section 10. If nivolumab is held at any timepoint, study calendar assessments for that day should be repeated prior to re-initiation of

CONFIDENTIAL

This document is confidential. Do not disclose or use except as authorized.

nivolumab.

Table 17 Dose Delay Instructions

	To be resumed within window?	Lenalidomide	Dexamethasone	Nivolumab
Nivolumab delayed on Day 1 of Cycle	N/A	To be delayed until Nivolumab is resumed	To be delayed until Nivolumab is resumed	Resume dosing= new Day 1 of Cycle
Nivolumab held on Day 15 of Cycle	Yes	Dosing to continue as scheduled	Dosing to continue as scheduled	Resume dose any day within window; dose time point not skipped
Nivolumab held on Day 15 of Cycle	No	Dosing to continue as scheduled	Dosing to continue as scheduled	Resume dosing at next dosing time point

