Study Drug Administration	
Agent Administration Guidelines are found in Section 5.2
 
 • Nivolumab is given IV every other week on Days 1&15; Lenalidomide is PO Days 1-21; Dexamethasone is PO Days 1, 8, 15 for Cycles 1-6 ONLY • Nivolumab is given IV over 60 minutes (+/- 10 minutes); No standard premeds required, unless history of infusion reaction. A 60 min post-infusion observation period is suggested, especially during first 2 cycles, but not mandatory per protocol. • The drugs may be administered in any order. • Criteria to treat DAY 1: ANC\geq1,000; PLT\geq50; Other drug related, non-heme tox \leqGrade 1 or baseline. • Criteria to treat DAY 15: For Lenalidomide: ANC\geq1,000; PLT\geq30; Hgb\geq8 Other drug related less than Grade 3 or baseline. For Nivolumab: AST\leq90; ALT\leq156; Bilirubin\leq1.8; Creatinine\leq1.95 or \leq1.5 x baseline • Fasting is not required. • Lenalidomide capsules and Dexamethasone tablets should be swallowed whole, and should not be broken, chewed or opened. Administration should be at approximately the same time each day. If a dose is missed and less than 12 hours has elapsed since the missed dose, the patient may take the dose for that day. If more than 12 hours has elapsed since missing a dose at the normal time, the patient should not take the dose, but take the next dose at the normal time on the following day. If a dose is missed, it should be taken as soon as possible on the same day. If a dose is vomited, the dose should not be made up and the participant should continue with the regular schedule of the drug at the next dose.
Dose Mods & Toxicity	
Dose Modifications/Dosing Delay for Toxicity are outlined in Section
 
 • This protocol uses NCI CTCAE criteria, version 4.03 • There are no dose modifications for Nivolumab, there are dose reductions per protocol for Lenalidomide and Dexamethasone.
Con Meds	
Concomitant Therapy Guidelines are in Section 5.3.1
 
 • Stem cell mobilization and collection may be performed at time of best response or after 6 cycles of therapy. • Filgrastim is allowed, pegfilgrastim is NOT. • Transfusions and supportive care are allowed; bisphosphonate therapy included.

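### The nursing page's Day 15 lenalidomide criterion lets dosing continue at related renal/metabolic Grade 2, where Table 13 requires a hold

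*Combined protocol and SAP*

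**What the plan says.** Section 6.3, Table 13, has a Renal/Metabolic row. At Grade 2 the action is "Hold Lenalidomide until < grade 2 and resume treatment at the same dose level". At Grade 3 or 4 it is "Hold Lenalidomide until < grade 2 and resume treatment with one dose level reduction". The Grade 3 or 4 cell then covers toxicity that stays at Grade 3 or above, where the instruction is to "omit dose and restart at subsequent scheduled visit with one dose level" reduction, and it closes with "If treatment-related toxicity occurs on day one of the cycle, the cycle will be delayed".

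For the start of any cycle, Section 6.1 adds: "All other clinically significant, study drug related non hematologic toxicity must have resolved to" Grade 1 or lower, or baseline.

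The nursing page (special nursing considerations, Study Drug Administration) lists separate criteria for Day 1 and Day 15. Its Day 15 lenalidomide list gives limits for neutrophils, platelets and hemoglobin and ends with a general line, after which the nivolumab list begins: "Other drug related less than Grade 3 or baseline. For Nivolumab". The only creatinine limit on the page is in the nivolumab list.

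**The concern.** A patient part-way through a cycle with related renal/metabolic toxicity at Grade 2 meets two rules. Table 13 says hold. The nursing page says the lenalidomide criterion is met. The same split arises for an event first graded 3 or 4 that has come down only to Grade 2.

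At stake is exposure to lenalidomide during an unresolved renal/metabolic toxicity. Section 7.2.1.3 lists dehydration and renal failure among lenalidomide's risks. Section 5.1 lets participants stay on lenalidomide after the September 2017 clinical hold, so the dosing rule is still in use.

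**Working it through.** No sample size, error rate or event count is involved, so the check sets the texts side by side. All cases are toxicity judged related to lenalidomide in the renal/metabolic category.

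- **Day 1, Grade 2.** Table 13's Grade 2 cell holds. Section 6.1 does not allow the cycle to start unless Grade 2 is the baseline condition. The nursing page's Day 1 line uses the same limit as Section 6.1. These agree, apart from the baseline clause.
- **Day 1, Grade 3 or 4.** Table 13 holds and its last line delays the cycle. Section 6.1 and the nursing Day 1 line also stop treatment, with the same baseline clause. These agree.
- **Day 15, Grade 3 or 4.** Table 13 holds. The nursing line does not pass, unless that grade is the baseline. These agree apart from the baseline clause.
- **Day 15, Grade 2.** Table 13 holds until below Grade 2. The nursing line passes, because Grade 2 is below Grade 3. **Conflict.**
- **Within a cycle, Grade 3 or 4 improved to Grade 2.** Table 13's first sentence still bars restart. Its next sentence addresses toxicity still at Grade 3 or above and is silent on this case. The nursing line passes. **Conflict.**

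Three features suggest an omission on the nursing page and not a deliberate choice.

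1. The page otherwise follows the protocol. Its Day 15 platelet limit of 30 and hemoglobin limit of 8 match Table 12, and its Day 1 list matches Section 6.1.
2. The general line resembles Table 13's residual row, which continues treatment at Grade 2 unless the finding is clinically significant. That row covers only toxicities not named earlier in the table, and renal/metabolic is named earlier.
3. The page says lenalidomide dose reductions follow the protocol. The Grade 2 renal/metabolic action is a hold with return at the same dose, so that pointer does not reach it.

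**The case against.** The strongest reply is that the conflict has little room to occur.

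- Section 6.5 says "Required study schedule assessments should always correlate with the nivolumab dosing schedule", nivolumab has been stopped for all patients (Section 5.1), and the Section 10 calendar lists on-treatment visits on Day 1 only.
- Lenalidomide is an oral drug supplied per cycle (Section 8.2.8). No Day 15 dispensing is described, so the decision is whether the patient is told to keep taking it.
- Section 6.3 requires the treating investigator to judge clinical significance and "attribution to study medications before a treatment decision is made". Table 13 is to be followed unless the overall principal investigator approves a departure.
- While nivolumab was given, its creatinine limit would have flagged many such events, and Section 6.2 then asked the investigator whether to skip lenalidomide. This was not a full block, since Table 17 continues lenalidomide as scheduled when nivolumab is held on Day 15.
- Some pages next to the nursing page are not in the text available for review, so a statement that the protocol takes precedence cannot be excluded.

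All of this stands as a limit on reach. It does not make the two instructions agree.

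A reader might also infer that Table 13 lets lenalidomide restart at the next visit while toxicity is still Grade 3 or 4, or that the cell has no recovery grade. The documents do not support either reading. The sentence just before sets recovery to below Grade 2 and can be read as still governing. With nivolumab stopped, the next calendar visit is normally Day 1 of a cycle, where Section 6.1 applies.

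**Conclusion.** Wrong as written, at low severity: the nursing page states a Day 15 lenalidomide criterion that contradicts the governing dose-modification table for related renal/metabolic Grade 2, including Grade 3 or 4 events that have improved only to Grade 2. The conflict is confined to within-cycle decisions.

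This rests on the two texts as they stand and on no precedence statement in the missing pages. The documents give no basis for counting the patients or doses affected. It would be too strong to infer that participants were dosed through renal toxicity, or that the primary endpoint or any analysis is affected. The silence in Table 13's restart sentence is a drafting ambiguity and not a second defect.

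**What to change.** Add to the nursing page's Day 15 lenalidomide criteria: *renal/metabolic toxicity < Grade 2 per Table 13*.

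Optionally, add *once < grade 2* to Table 13's restart sentence for toxicity that remains at Grade 3 or above, so that it repeats the recovery grade already set in that cell.

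The cost is one line on the nursing page and, if taken up, a few words in one table cell. A few patients may have slightly longer lenalidomide holds. No assessment is added and no analysis changes.
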